3.2 Amniotic fluid (AF): Preclinical Data

Early after conception and until the mother's water breaks for the delivery of their infant, the fetus is bathed in amniotic fluid. AF functions as a supportive cushion to the fetus and provides a protective environment. AF is a rich source of nutrients, cytokines and growth factors that are required for fetal development and maturation.¹² AF also contains stem cells with the potential to differentiate along multiple cell lineages.^{13, 14} The protective and regenerative properties of AF are achieved via the exchange of water and solutes with surrounding tissues. This is accomplished via the utilization of different pathways during the course of a pregnancy that likely contribute to changes in the composition of the AF with gestational age.¹² A report that concentrates of AF inhibited the development of peritonitis was among some of the first evidence that AF had protective biological properties.¹⁵ This was followed by a publication by Shimberg and co-workers that AF accelerates defense-repair mechanisms within damaged joints.^{15, 16} Since these early publications, more sophisticated evaluations have revealed the presence of antimicrobial, immunomodulatory, and growth-

promoting activities in AF.¹² Reports about antimicrobial activity in AF differs¹⁷ among investigators. Some studies show that AF is inhibitory, while others show no effect against the same microorganisms. Yet, other reports provide evidence that AF with low antimicrobial activity is associated with a high incidence of an infectious syndrome in pregnant women.¹⁸ Components with antimicrobial, antiviral and antifungal activity that are present in AF include lysozyme, peroxidase, transferrin, -lysin, immunoglobulins and zinc-peptide complexes.¹⁷ Immunomodulatory properties of AF are evident from studies showing that enteral feeding of AF suppresses the pro-inflammatory responses in preterm pigs with necrotizing enterocolitis.¹⁹ While growth promoting activities of AF are supported by animal studies as well as by in vitro studies showing that AF can enhance neochondrogenesis,²⁰ regenerate peripheral nerves²¹ and bone,²² accelerate re-epithelialization in corneas,²³ and promote healing of human skin wounds.²⁴ Some of the factors that are found in AF that may contribute to these activities include inflammatory mediators that include, but are not limited to TNF-a, IL-6, IL8, and IL-10,²⁵ trophic factors that include EGF, IGF-1, FGF, HGF and TGF-a,²⁶⁻³⁰ and HA, an important factor in promoting re-epithelialization in human skin wounds.²⁴

Based on the hypothesis that nutrients, cytokines and growth factors contained in the non-cellular fraction of AF are useful for reparative and regenerative treatments in patients, Pierce et al conducted a study at the University of Utah to address three issues. The first was to determine the feasibility of consenting and screening volunteer donors for the routine collection of AF from full-term pregnant women scheduled for caesarean-section (C-sections) and then processing the AF for clinical applications. The second aim was to develop a processing method that resulted in a cell-free AF preparation suitable for clinical applications. The third goal was to gain a better understanding about components of AF procured from full-term pregnancies. With the above 3 goals in mind, human AF was collected by the staff of the Obstetrical and Gynecological department at the University of Utah hospital and was processed by technical staff of the Cell Therapy and Regenerative Medicine (CTRM) facility at the University of Utah. Physician executed abdominal incisions were performed through the abdominal and uterine muscles without cutting into the amnion membrane. Using a sterile soft suction catheter connected to a sterile MediVac Suction Container (Cardinal Health, Waukegan, IL), a blunt end insertion with a catheter was made into the amnion membrane and the AF was aseptically suctioned into a MediVac Container. The container was labelled, wrapped in frozen Insul-ice mats (Fisher Scientific, Hanover Park, IL) and placed in a temperature-monitored shipper that was validated for transport between 2 and 8 °C. The AF was transported to the CTRM facility at the University of Utah. Upon arrival at the CTRM facility, the product was immediately placed into a refrigerator at 2–8 °C until processing occurred. At the time of processing, the MediVac container with AF was aseptically placed in a biological safety cabinet and the AF was transferred via aseptic techniques into sterile centrifuge tubes. The total volume and gross appearance of the AF were recorded and samples were removed for sterility testing, cell counts and other relevant testing. The AF was centrifuged at 1400×g for 20 min at 4 °C. Once centrifugation was complete, the supernatant was expressed into a new transfer pack and the remaining cell pellet was characterized and cultured as described below. The supernatant from the AF was processed using a proprietary filtration technology to sterilize and eliminate cellular debris from the final product. AF collections and final products were evaluated for total volume, fluid chemistries, total protein, and hyaluronic acid (HA) levels. Final products of processed AF (pAF) were also assessed for their cellular content and for their protein profiles using quantitative antibody arrays.

To validate the above described approach for collecting and processing AF, 36 pregnant women consented and passed the donor screening criteria. AF was successfully collected from 17 individuals. Median AF volumes were 70 mL (range 10–815 mL; $n = 17$). Fluid chemistries were similar, but some differences were noted in HA levels and cytokine profiles. Cytokine arrays revealed that an average of 304 ± 20 (mean \pm SD; $n = 3$) of 400 proteins tested were present in AF with a majority of cytokines associated with host defense. Some of the peptides encountered and classified according to their function are found on Table 1.

Pro-inflammatory	OPN, PAI-I, CD163, RAGE, IL17, IL1R3
Host defense	IL-27, LAG-3, GITR, PD1
Innate Immunity	hCGB, Galectin-3, TLR-2, Osteoactivin
Antimicrobial	TSP-1, lactoferrin, CXCL14, Trappin-2, CCL-28, MIG
Anti-inflammatory	IL1-ra, MBL
Embryonic development	DKK1, DKK3
Angiogenesis	VEGF R1, Transferring, TIMP-2
Wound healing	OPN, PAPP-A, FAP

Table 1: List of Peptides according to their function

5 Study Design and Procedures

This is a randomized, double-blinded, placebo-controlled study of the efficacy of pAF in patients with hematologic malignancies who have undergone Allogeneic Hematopoietic Stem Cell Transplantation (HSCT) and are diagnosed with chronic GVHD of the eye. Patients will be allowed to continue the use of non-medicated lubricant eye drops (artificial tears) for ocular GVHD treatment prior to participating in this study. Patients are allowed to resume the use of eye drops after the 30 day treatment period at the discretion of the treating physician.

5.1 Dosage

pAF will be given as one drop (50 μ L) in one eye twice daily and saline (placebo) will be given as one drop in the second eye twice daily for a total of 30 days. Patients will be instructed to treat their eyes once in the morning and once in the evening. In patients wearing bilateral scleral lenses, the drops will be applied prior to lens insertion in the morning and immediately after removal at night.

The assignment of which eye gets which drop will be randomly selected. Neither the patient nor their doctors will know which eye is receiving AF and which eye is receiving placebo. The eyedropper bottles containing pAF and placebo (i.e. physiological saline) will be packaged the same.

5.2 Patient Study Calendar

	Screening/ Baseline	Day 30±3 days ⁶	Day 60±3 days ⁶	Day 100±3 days ⁶	Early Discontinuation of Study Drug
Informed Consent	×				
Eligibility	×				
Medical History	×				
Concomitant meds	×	×	×	×	×
Randomization	×				
Dispense Drug	×				
Physical Exam	×	×	×	×	×
Drug Compliance		×			
FACT G (QOL)	×	×	×	×	×
DEWS assessment	×	×	×	×	×
NIH CC Response Assessment for Chronic GVHD ^{1,3}	×	×	×	×	×
Complete Eye Exam ^{2,3}	×				
Urine Pregnancy Test ⁴	×				
FU Eye Exam ²		×	×	×	×
Adverse Events		×	×	×	×
Review Study Diary ⁵		×	×		×

¹ Health Care Provider Global Rating, Eye Score, Patient Global Rating

² Including DEWS assessment by ophthalmologic assessment and visual acuity

³ The NIH CC Response Assessment for Chronic GVHD and the Complete Eye exam can be performed within seven days of each other.

⁴ Pregnancy test is required if participant is of childbearing potential.

⁵ The study team may call the participant before the 30-day visit to address diary questions and completion.

⁶ Follow-up visits may be conducted via phone call if in-person visits cannot be completed.

Table 2: Schedule of Events

5.3 Drug Dispensation and Randomization

Upon acceptance into the study, the CTRM facility will be notified and the patient will be randomized as to which eye will receive the drug and which will receive the placebo. Randomization will be done using the MS Excel randomization method. Based on the results of the randomization selection, CTRM will then select appropriate coded boxes. Four boxes containing 8-eyedropper bottles per box will be labeled with a yellow dot and stamped with an “R” for right eye. Each eyedropper bottle is labeled with a yellow dot and stamped with an “R”. Four boxes containing 8-eyedropper bottles per box will be labeled with a blue dot and stamped with an “L” for left eye. Each eyedropper bottle is labeled with a blue dot and stamped with an “L”. The boxes will be labeled as Amniotic Fluid Eye Drops, each set (right and left) will contain a total of 32 eyedropper bottles of pAF and 32 eyedropper bottles of placebo.

The boxes will be packaged on dry ice and transported to the patient. The patient will be provided with the instructions on how to store the eye drops at home, how to use the eye drops and how to handle the dry

ice. The patient will transport the eye drops to their home and immediately transfer them to their kitchen refrigerator freezer. For each day of use the patient will dispense the eye drops as follows:

1. The patient will remove a single right eye and left eye, eyedropper bottle from the freezer. They will verify that the lot number on the eyedropper bottles match the labels on the box it was removed from.
2. They will thaw the frozen fluid in the eyedropper bottles by placing the bottle in their hand or by placing it at room temperature until the entire volume is completely thawed.
3. For the 1st daily application (e.g., morning), they will remove the eye dropper bottle cap from the eyedropper bottle labeled right. Invert bottle over the right eye and squeeze the bottle to dispense 1 drop into the right eye. They will then tightly cap the eyedropper bottle.
4. They will then remove the eye dropper bottle cap from the eyedropper bottle labeled left and invert the bottle over the left eye and squeeze the bottle to dispense 1 drop into the left eye. They will then tightly cap the eyedropper bottle.
5. They will refrigerate both bottles containing remaining pAF at temperatures between 1 °C and 10 °C (e.g., refrigerator). They will not re-freeze the fluid in the bottles
6. For the 2nd daily application, they will remove the same eyedropper bottles that they used in the morning from the refrigerator and repeat steps 7 & 8.
7. After the second application, they will place both eyedropper bottle into a box that was provided to them for the placement of bottles that had been used.
8. The patient will repeat these steps for each daily application.
9. After the 30 day treatment the patient will return all used and unused bottles to the clinic.

The patients will be instructed to return all used and unused vials along with their diary. This will allow us to account for drug dispensed and monitor compliance.

5.4 Concomitant Medications and Procedures

Only medications with ocular effects will be recorded at screening and at subsequent study visits. These medications will be recorded in the medical record and appropriate CRF.

Patients may use non-medicated saline eye drops (artificial tears), provided they are applied in both eyes greater than 30 minutes following the application of the study eye drops.

All other eye drops, other than non-medicated saline eye drops, are prohibited while the patient is on study. If the patient is on medicated eye drops, a seven day washout is required before starting treatment. Patients can enroll if they have bilateral punctal plugs or if puncta were previously thermally cauterized, but the insertion of punctal plugs or cauterization is not allowed while the subject is on study.

5.5 Assessment of Response:

Assessment of response will be performed at 30 ± 3 , 60 ± 3 and 100 ± 3 days after initiation of therapy with pAF. The response is a combination of the NIH CC assessments and the ophthalmologic assessment (DEWS evaluation) as follows:

- NIH Consensus Conference (CC) for assessment of response in chronic GVHD
- Ophthalmologic assessment: Dry eye assessment will be performed over the course of four eye exams, including a baseline comprehensive eye exam (including a dilated fundus examination), and three follow-up exams (without dilation) on Day 30 ± 3 , Day 60 ± 3 and Day 100 ± 3 . Signs and symptoms of dry eye will be assessed at each exam using the grading scale provided by the International Dry Eye Workshop (DEWS) 2007 report.¹ DEWS assessment will include visual symptoms, severity and frequency of discomfort, conjunctival injection, conjunctival staining (using NaFl), corneal staining (using NaFl), corneal/tear signs (including filamentary keratitis and debris), the eyelids and meibomian glands, and fluorescein tear break-up time (TFBUT). Each sign/symptom will be graded on a scale of 1 to 4, with 4 being most severe. A total score will be taken at each exam, and a cumulative decrease in overall score >2 will constitute improvement with treatment. Note: Schirmer testing will not be performed or graded, as it has no proven value in ocular chronic GVHD.

Responders would be defined as a one point improvement in the dry eye grading scale (DEWS), without worsening in the eye score (NIH Consensus Criteria Ocular Assessment).

5.6 Assessment of Secondary Endpoints:

This includes the measurement of QOL with the FACT-G tool, patient reported pain assessment and measurement of visual acuity by ophthalmology.

5.7 Assessment of Safety:

Safety and tolerability will be evaluated by the investigator from the results of reported signs and symptoms, scheduled physical examinations, vital sign measurements, and clinical laboratory test results done as standard of care at day 30 ± 3 , day 60 ± 3 and day 100 ± 3 after initiation of pAF therapy. More frequent safety evaluations may be performed if clinically indicated or at the discretion of the investigator. SAEs will be reported within 24 hours of discovery to the central Data Coordinating Center.

Toxicity will be reported using Common Terminology Criteria for Adverse Events (CTCAE) version 4. Only ocular AEs will be collected.

An AE may consist of the following:

1. A new event which was not pre-existing at initial study drug administration.
2. A pre-existing event which recurs with increased intensity or increased frequency subsequent to study drug administration.

3. An event which is present at the time of study drug administration which is exacerbated following initial study drug administration.

A Serious Adverse Event (SAE) is defined by FDA and NCI as any adverse drug event (experience) occurring at any dose that in the opinion of either the investigator or sponsor results in any of the following outcomes:

1. Death
2. Life-threatening adverse drug experience
3. Inpatient hospitalization or prolongation of existing hospitalization (for > 24 hours)
4. Persistent or significant incapacity or substantial disruption of the ability to conduct normal life functions
5. Congenital anomaly/birth defect
6. Important Medical Event (IME) that may not result in death, be life threatening, or require hospitalization may be considered a serious adverse drug experience when, based upon medical judgment, it may jeopardize the patient or subject and may require medical or surgical intervention to prevent one of the outcomes listed in this definition

IRB Notification: Events meeting the University of Utah IRB reporting requirements (<http://www.research.utah.edu/irb/>) will be submitted through the IRB's electronic reporting system within 10 working days.

Reporting will be performed according to FDA guidance (<https://www.fda.gov/downloads/regulatoryinformation/guidances/ucm126572.pdf>)

5.8 Discontinuation of Study Drug:

The study drug will be discontinued if any of the following occur:

- Significant worsening of ocular chronic GVHD during the treatment period. This decision will be at the discretion of both the treating transplant physician and ophthalmologist.
- Study drug can be discontinued by the study participant prior to the Day 30±3 clinic visit, in which case the Early Discontinuation of Study Drug visit will occur.
- Discovery of new information which makes the subject ineligible to continue participation in the study.
- Any other condition that in the opinion of the treating physician and ophthalmologist are not compatible with participation in this study.
- A subject may withdraw their consent at any time without affect to their care.

5.9 Discontinuation of Study:

Significant worsening of ocular chronic GVHD in the eye treated with amniotic fluid over a period of 30 days, in >8 patients.

- The determination of the number of patients meeting this criteria will be performed by 1 designated person in CTRM, who will be the only one unblinded. Thus, the blind will not be broken throughout the study.

6 Statistical Considerations

Analysis of the primary endpoint will be coded as each having responded or not responded at the 30 day visit. Because a participant's eyes are more likely to be similar compared to eyes from two different participants we will conduct a paired analysis using McNemar's test. Assuming a significance level of 0.05, and a response rate in the control eye of 5%, 15 participants will provide 80% power to detect a difference if the response in the treated eye is 60%. With 19 participants we will have 80% power to detect a response rate of 50%. Due to the small sample size it is likely an exact p-value will be calculated.

The impact of different covariates on ORR will be analyzed using descriptive statistics, Wilcoxon rank sum test, and Fisher's exact test where applicable. Differences in NIH Eye and DEWS scores will be analyzed using Wilcoxon signed-rank test.

The proportion of subjects who experience adverse events and serious adverse events will be summarized descriptively; no inferential tests will be performed.

7 Data Management

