Diagnosis and Main Eligibility Criteria	
Inclusion:
 
 1. Patients diagnosed within 5 years after hematopoietic stem cell transplant for any disease, with any graft and any conditioning regimen with at least one of the following: 
 • Dry eye symptoms partially affecting (requiring lubricant drops > 3 × per day, punctal plugs, or thermally cauterized puncta) or significantly affecting (special eyewear to relieve pain) activities of daily living (ADL). • Unable to work because of ocular symptoms. • Loss of vision due to keratoconjunctivitis sicca (KCS). Patients may be using bilateral scleral lenses and/or bilateral punctal plugs at the time of accrual. 2. Patients who are 18 years of age or older. 3. Willing and able to provide informed consent. 
Exclusion:
 
 1. Patients who have any other reversible cause for dry eye at the time of accrual. 2. More than 3 lines of therapy beyond corticosteroids with or without calcineurin inhibitors or sirolimus. 3. Relapsed malignancy at time of accrual after the most recent transplantation. 4. A difference in dryness between both eyes of more than 2 points of the grading provided by the International Dry Eye Workshop (DEWS) 2007 report.¹ 5. Patients who are pregnant or plan to become pregnant while participating in the study. 6. Patients who are not willing to discontinue the use of any eye drops, with the exception of non-medicated lubricant eye drops (artificial tears). All eye drops (excluding non-medicated lubricant eye drops) must be stopped at least seven days before treatment with pAF. 7. Inability to comply with the investigational plan and visit schedule for any reason, in the judgement of the investigator.

Continued on next page

Continued from previous page

Study Product, Dose, Route, Regimen	
pAF will be given as one drop in 1 eye and saline (placebo) will be given in the other eye. pAF and placebo will be used in each eye twice daily, for a total of 30 days.
 
In patients wearing bilateral scleral lenses, the drops will be applied prior to lens insertion in the morning and immediately after removal at night

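### Section 5.8 stops study drug for worsening during the 30-day course, but no safety contact is scheduled between baseline and Day 30±3, when 90–100% of the course has been given.

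*Protocol*

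**What the plan says.** **Treatment.** The Synopsis states: "pAF and placebo will be used in each eye twice daily, for a total of 30 days". Section 5.1 agrees. The drops are self-administered at home (section 5.3).

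**Stopping rule.** Section 5.8 says study drug will be stopped on several grounds. The first reads: "Significant worsening of ocular chronic GVHD during the treatment period. This decision will be at the discretion of both the treating transplant physician and ophthalmologist". The section names no visit, score or other measurement to inform that decision.

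**Scheduled looks.** Section 5.5 sets a baseline eye exam and then "three follow-up exams (without dilation) on Day 30 ± 3 , Day 60 ± 3 and Day 100 ± 3". Section 5.7 bases the safety evaluation on reported signs and symptoms, physical exams, vital signs and laboratory tests "done as standard of care at day 30 ± 3 , day 60 ± 3 and day 100 ± 3 after initiation of pAF therapy". Table 2 has no column between Screening/Baseline and Day 30±3. Its rows for adverse events, follow-up eye exam and diary review all begin at Day 30, apart from the Early Discontinuation column.

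**What is allowed earlier.** Footnote 5 to Table 2 reads: "The study team may call the participant before the 30-day visit to address diary questions and completion". Section 5.7 permits additional safety evaluations when there is a clinical reason or when the investigator chooses. If a participant stops drug early, the Early Discontinuation visit collects adverse events, an eye exam and the diary.

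**The diary.** Under SAP section 3.4 participants keep it daily and note issues with the drops. Under SAP section 6.3.6 it also supplies pain scores for each eye, analysed against day of treatment.

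**The concern.** A rule for stopping treatment is useful only if information reaches the people who apply it while treatment is still running. Here two physicians must judge whether the disease has worsened during a 30-day course, and the schedule gives neither of them a planned look until the course is over or nearly over.

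This matters more than usual for three reasons. The trial is Phase I/II, and safety is its first-listed primary objective. Participants must stop medicated eye drops at least seven days before treatment, and these stay barred during it, so worsening in either eye is foreseeable. Drops are taken at home, so staff have no incidental sight of the eyes.

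At stake is timely detection. A participant who worsens but does not call could receive nearly the whole course before anyone is due to ask.

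**Working it through.** The plan gives no figure of its own to reproduce on this point. The check sets the visit windows against the dosing period.

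**Inputs**
- Course length: 30 days (Synopsis; section 5.1).
- Frequency: 2 applications per eye per day (same places), so 2 × 30 = 60 per eye.
- First scheduled safety visit after baseline: Day 30±3, that is Day 27 to Day 33 from the start of therapy (sections 5.5 and 5.7; Table 2).

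**Formula.** For a first visit on day v, treated days = min(v, 30), share of course = min(v, 30)/30, and applications per eye = 2 × min(v, 30). The day of the visit is counted as a completed dosing day.

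| First visit | Share of course | Applications per eye | Position |
|---|---|---|---|
| Day 27 | 27/30 = 90% | 2 × 27 = 54 of 60 | 3 treatment days left |
| Day 30 | 30/30 = 100% | 2 × 30 = 60 of 60 | course complete |
| Day 33 | 30/30 = 100% | 60 of 60 | 3 days after the end |

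The first scheduled look therefore comes after 90–100% of treatment. It falls inside treatment only if held on Day 27, 28 or 29, with 3, 2 or 1 days left.

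**Provisions that could act earlier**
- Footnote 5 call: permitted, not required. Its stated purpose is the diary, and Table 2 attaches no adverse-event question to it.
- Additional evaluations under section 5.7: discretionary, with no time or trigger stated.
- Early Discontinuation visit: has the right content, but takes place once drug has been stopped, so it follows the decision.
- Diary: written during exposure, but Table 2 marks its review only at Day 30, Day 60 and Early Discontinuation.

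None of the four is a scheduled safety contact before Day 30±3.

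**A further point.** Footnote 6 lets follow-up visits, including Day 30, be held by phone when attendance is not possible. In that case the first scheduled in-person eye exam could be the Day 60±3 visit (Day 57–63), which is 57 − 30 = 27 to 63 − 30 = 33 days after the course ends.

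**The case against.** The best defence is that section 5.8 is an event-driven rule left to clinical judgement. It is tied to no scheduled measurement, so no passage strictly contradicts another. Section 5.7 gives the investigator a free hand to evaluate earlier, and that route does not require a complaint from the participant. The Early Discontinuation visit then documents what happened. In addition, the consent pages and some protocol text are not in the material reviewed, and instructions to participants on reporting problems may be there.

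Much of this stands. It rules out four stronger conclusions that a reader might infer:

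- **That no scheduled assessment can fall inside treatment.** A visit on Day 27–29 does.
- **That the rule cannot operate before the last dose.** It can, through a participant's report, investigator discretion, the optional call, or a visit early in the window.
- **That all adverse events from the exposure period rest on recall.** The diary captures issues as they occur and pain by eye. The weakness is late review of the diary.
- **That the section 5.9 count or the safety analysis depends on onset time.** Section 5.9 counts worsening of the pAF-treated eye over 30 days, which a Day 30 exam against baseline can supply. The safety analysis is a descriptive proportion of subjects with events (protocol section 6; SAP section 6.4).

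The defence does not supply a planned input to the rule. Discretion with no stated time or trigger may never be exercised, and whatever participants were told about reporting, Table 2 shows no scheduled contact.

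**Conclusion.** The point holds as a gap between a stopping rule and the schedule meant to support it. No safety contact, adverse-event query, eye exam or diary review is scheduled between baseline and Day 30±3, when 54–60 of 60 applications per eye (90–100%) have been given. Earlier detection is possible but rests on participant reports or staff discretion.

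The figures assume that dosing starts on the first study day and runs uninterrupted for 30 days, and that the visit is held within its window. The conclusion also assumes that no separate monitoring or contact schedule exists in text not available here. Reporting instructions to participants, if they exist, would improve the participant-initiated route but would not create a scheduled one.

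This is worth correcting because it bears on safety detection and the remedy is cheap. It does not affect the McNemar analysis or the sample size, and it gives no ground for calling the safety analysis or the section 5.9 rule unworkable.

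**What to change.** Reconcile sections 5.7 and 5.8 and Table 2, so that the rule on worsening during treatment has a planned source of information. One option uses a contact the protocol already permits:

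- make the footnote 5 call required and give it its own column in Table 2;
- tick the Adverse Events row for it, with the question asked separately for the right and left eye, which keeps the blind;
- review the diary, including the pain scores, at that contact.

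The timing of the call, what happens after a reported problem, and every stopping criterion are for the sponsor to set.

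The cost is a short protocol amendment and coordinator time for one call per participant, 15–20 calls at the planned enrolment. The limitation is that a call yields symptoms only. It does not replace an eye exam, so the ophthalmologist's part of the section 5.8 judgement would still need a visit where the sponsor considers one necessary.
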